**STUDY SYNOPSIS**

Study Title	A Randomized, Open-Label, Multicenter Study of Liposomal Amikacin for Inhalation (LAI) in Adult Patients with Nontuberculous Mycobacterial (NTM) Lung Infections caused by Mycobacterium avium complex (MAC) that are refractory to treatment
Name of Test Drug/ Investigational Product	Liposomal Amikacin for Inhalation (LAI)
Active Pharmaceutical Ingredient	Amikacin sulfate
Objectives	
Primary Objective
 
 
To evaluate the efficacy of LAI (590 mg) administered once daily (QD), when added to a multi-drug regimen, for achieving culture conversion (3 consecutive monthly negative sputum cultures) by Month 6 compared to a multi-drug regimen alone
 
 
Secondary Objectives
 
 
To evaluate the efficacy of LAI (590 mg) administered QD when added to a multi-drug regimen on the six-minute walk test (6MWT) at Month 6 compared to a multi-drug regimen alone
 
To evaluate the efficacy of LAI (590 mg) QD when added to a multi-drug regimen on the durability of treatment success 3 months after the end of total treatment course (negative sputum culture after 3 months off treatment)
 
To evaluate the efficacy of LAI (590 mg) administered QD when added to a multi-drug regimen for time to culture conversion compared to a multi-drug regimen alone
 
To evaluate the efficacy of LAI (590 mg) administered QD, when added to a multi-drug regimen for achieving sustainability (consecutive negative sputum cultures [with no more than 2 consecutive monthly broth positive cultures] for 12 months on treatment) compared to a multi-drug regimen alone
 
To evaluate the efficacy of LAI (590 mg) administered QD when added to a multi-drug regimen on the 6MWT at End of Therapy (EOT) compared to a multi-drug regimen alone
 
To evaluate patient-reported symptoms of NTM and change from Baseline (Day 1) in quality of life scores on the St. George's Respiratory Questionnaire (SGRQ) at Month 6
 
 
Exploratory Objectives

Protocol Amendment #3 version: 22 February 2016

	
 
1. To evaluate the change from Baseline to Month 6 on the 6MWT for converters versus non-converters within the LAI (590 mg) administered QD added to a multi-drug regimen arm
 
2. To evaluate the change from Baseline to Month 6 on the 6MWT for converters versus non-converters for all subjects
 
3. To evaluate the change from Baseline to Month 6 on the 6MWT for converters versus non-converters within the multi-drug regimen alone arm
 
4. To evaluate the change from Baseline to Month 6 on Body Mass Index (BMI) for those randomized to LAI (590 mg) administered QD added to a multi-drug regimen compared to a multi-drug regimen alone
 
5. To evaluate the efficacy of LAI (590 mg) administered QD when added to a multi-drug regimen on the 6MWT at Month 8 and 3 months off-treatment compared to a multi-drug regimen alone
 
6. To evaluate the proportion of subjects achieving culture conversion with durability after 12 months off treatment (EOS) in the LAI arm compared to a multi-drug regimen alone
 
7. To compare patient-reported symptoms of NTM and change from Baseline (Day 1) in quality of life scores on the SGRQ – Part 2 (Activities of Daily Living) at Month 6
 
8. To compare change from Baseline (Day 1) in the EQ-5D-3L patient reported health outcomes at Month 6 and EOT
 
9. To evaluate the number of subjects in each treatment arm who develop a new strain of MAC during the study at EOS
 
10. To compare all-cause mortality between treatment arms 12 months after treatment (EOS)
 
 
Safety Objective
 
 
1. To evaluate the safety and tolerability of LAI (590 mg) QD added to a multi-drug regimen arm
 
 
Pharmacokinetic Objectives
 
 
1. To evaluate the pharmacokinetics (PK) of LAI via a population PK approach
 
2. To evaluate the concentration of amikacin in sputum after 2 days interruption of LAI dosing in a subset of subjects
 
3. To evaluate the concentration of amikacin in sputum after 28 days off-LAI in a subset of subjects
 
4. To evaluate the concentration of amikacin in sputum after 3 months off-LAI in a subset of subjects
 
 
Comprehensive Pharmacokinetic Sub-Study Objectives

--	---

Protocol Amendment #3 version: 22 February 2016

*This protocol is solely for the purpose of communicating information about the investigational drug between Inmed Incorporated and study personnel. Information is not to be reproduced, abstracted or used for sharing of information for any other purpose, whatsoever, except with the written permission of Inmed Incorporated.*

Confidential

	
 
1. To characterize systemic amikacin exposure, including approximate systemic bioavailability in Japanese subjects, using a population PK model to describe the disposition of amikacin in the serum
 
2. To compare population PK modeling between Japanese subjects to historical population PK modeling for LAI
 
3. To evaluate the amikacin concentration in sputum
 
 
CT Scan Sub-Study Objective
 
 
1. To compare assessments of chest CT scans, read by a trained medical professional, from Baseline (Day 1) to EOT in a subset of subjects within each treatment arm
 

Study Description	
Study Rationale
 
Treatment guidelines for patients with MAC lung infection in the published American Thoracic Society/Infectious Diseases Society of America (ATS/IDSA) consensus document were based primarily on small uncontrolled or non-comparative studies in subjects with predominantly severe or refractory MAC disease [Griffith et al, 2007].
 
Overall, there remains a lack of sufficiently powered, prospective clinical trials aimed at the treatment of pulmonary MAC infection. Many of the drugs used in the prolonged, recommended multi-drug regimens are expensive and poorly tolerated [Ballarino, et al 2009]. It is clear from these single-site studies that there is an unmet need for more effective, less-toxic therapeutic options.
 
Study TR02-112 was a randomized double-blind placebo controlled study that dosed 89 subjects with LAI or placebo added to a background multi-drug regimen. At Day 84, 25.0% of subjects with add-on LAI had a negative sputum culture compared to 6.7% of subjects with add-on placebo. This is an important result in this population as subjects were refractory to therapy for a minimum of 6 months to more than 2 years prior to enrollment.
 
Study INS-212 will evaluate whether the signal identified in TR02-112 is further confirmed with a longer duration of LAI treatment in subjects with NTM MAC lung infections who are refractory to a stable multi-drug regimen for at least 6 months. INS-212 is a randomized, open-label study of efficacy, safety and tolerability of once daily dosing of 590 mg LAI plus a multi-drug regimen compared to a multi-drug regimen alone in subjects with NTM lung infections that are refractory to therapy. Eligible subjects are those diagnosed with MAC and with persistently positive cultures while being treated with a multi-drug treatment regimen (at least 2 antibiotics) for a minimum duration of 6 consecutive months that is either ongoing or completed no more than 12 months before Screening (exceptions to multi-drug treatment regimen for 6 consecutive months include treatment with doses or frequencies below those recommended by guidelines and/or short interruptions of therapy, both occurring due to safety/tolerability issues).
 
One to three sputum samples collected at Screening will be used to determine eligibility of the subject. At Baseline, subjects will start or continue on a multi-drug anti-mycobacterial regimen (at least 2 antibiotics) and will be randomized to LAI (590 mg) QD plus a multi-drug regimen or to a multi-drug regimen alone for a

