	
minimum of 8 months. Subjects who demonstrate culture conversion by Month 6 will complete a total treatment course of 12 months starting from the first of 3 negative cultures that defines culture conversion.
 
Randomization will be stratified according to subject smoking status (current smoker or not) and current multi-drug regimen status (on treatment or off treatment for at least 3 months) at Screening.
 
Design
 
The Screening window allows time for sputum culture results, susceptibility by minimum inhibitory concentration (MIC) determination, and scheduling of Screening assessments. Any delay in obtaining microbiological results and MICs must be reported to the Sponsor immediately and documented within the study source documents. In the event that sputum culture results are not known by 8 weeks (Day - 14), the Baseline (Day 1) visit should be scheduled as soon as possible in order to maintain the Screening window, and an extension of the Screening window to 14 weeks is allowed, if necessary. If sputum culture results are known prior to 8 weeks (Day -14), the Screening window of 10 weeks must be maintained. Once Screening assessments are complete and sputum culture results are known, eligible subjects will be randomized 2:1 to LAI administered QD plus a multi-drug regimen or a multi-drug regimen alone. The primary efficacy endpoint is the proportion of subjects achieving culture conversion (3 consecutive monthly negative sputum cultures) by Month 6 in the LAI plus a multi-drug regimen arm compared to a multi-drug regimen alone.
 
Converters are defined as subjects who have 3 consecutive monthly MAC-negative sputum cultures at any time within the first 6 months of the study. After culture conversion, relapse or recurrence is defined as having MAC-positive sputum cultures in liquid broth media (agar negative) for 3 or more consecutive months, or having 1 MAC-positive sputum culture on solid media (agar positive). Non-converters are defined as subjects who do not have 3 consecutive monthly MAC-negative sputum cultures at any time within the first 6 months of the study.
 
Sputum culture results will only be available to the site after the Month 6 sputum result is known, in time for the Month 8 visit. At Month 8 (-28 to +7 days), after all sputum culture results are known, up to and including Month 6, subjects will be assessed as converters or non-converters.
 
All converters will remain in Study INS-212. All converters who, after culture conversion, subsequently have MAC-positive sputum cultures in liquid broth media (agar negative) for 1 or 2 consecutive months only, will also remain in Study INS-212. These subjects will continue on their randomized treatment regimen until they complete a total of 12 months of treatment (EOT), starting from the first of 3 negative cultures that defines culture conversion. These subjects will return after the EOT visit for 28 day, 3, 6 and 12 months off-treatment follow-up visits. The 12 months off-treatment follow-up visit will be the end of study (EOS) visit. No NTM treatment will be administered during the off-treatment phase.
 
At Month 8, all non-converters will be discontinued from INS-212. All subjects who experienced a relapse or recurrence after culture conversion by Month 6 will also be discontinued from INS-212 at their Month 8 visit. These subjects may be eligible to

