Lipid/liposome delivery systems similar to that used to deliver LAI in this study have been used to improve the therapeutic index of several injectable therapeutic agents. In a liposome drug delivery system, a bioactive agent entrapped in a liposome is administered to the patient. Alternatively, drugs can be combined with lipids to form nonencapsulated lipid drug complexes having therapeutic advantages. Therapeutic properties of several commercial products, such as anticancer compounds liposomal doxorubicin (Doxcil®) and liposomal daunorubicin (Daunosome®) and the antifungal lipid complex of amphotericin B (Abelcet®, Ambisome®), have improved dramatically after encapsulation or complexing with a lipid. Although these commercial products are administered IV, inhaled Ambisome is being evaluated for prophylactic use.

Study TR02-112 was a randomized double-blind placebo controlled that dosed 89 subjects with LAI or placebo added to a background multi-drug regimen. At Day 84, 25.0% of subjects with add-on LAI had a negative sputum culture compared to 6.7% of subjects with add-on placebo. This is an important result in this population as subjects were refractory to therapy for a minimum of 6 months to more than 2 years prior to enrollment. Furthermore, 12 subjects demonstrated sustained negative culture results with add-on LAI to the end of the open-label phase (Day 168) including the 28 days off LAI follow-up period.

Protocol Amendment #3 version: 22 February 2016

*This protocol is solely for the purpose of communicating information about the investigational drug between Insmmed Incorporated and study personnel. Information is not to be reproduced, abstracted or used for sharing of information for any other purpose, whatsoever, except with the written permission of Insmmed Incorporated.*

Confidential

The change in subject functional status was assessed using the 6 minute walk test and a statistically significant difference in favor of LAI (a mean increase from Baseline [Day 1] of 23.859 meters vs. a mean decrease of 25.032 meters in the LAI vs. placebo arms, respectively ( $p = 0.0134$ )).

Study INS-212 will evaluate whether the signal identified in TR02-112 is further confirmed in a longer duration of LAI treatment in patient with NTM MAC lung infections who are refractory to a stable multi-drug regimen for at least 6 months.

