## 4.1 INCLUSION CRITERIA

To be eligible for enrollment, a prospective patient must meet all of the following criteria:

1. be male or female, 18 years or older (20 years or older in Japan)
2. be positive for MAC on culture as defined in inclusion criterion No. 4 while being treated with a multi-drug treatment regimen (at least 2 antibiotics) for a minimum duration of 6 consecutive months that is either ongoing or was stopped no more than 12 months before Screening (exceptions to multi-drug treatment regimen for 6 consecutive months include treatment with doses or frequencies below those recommended by guidelines and/or short interruptions of therapy, both occurring due to safety/tolerability issues)
3. be diagnosed with MAC NTM lung infection with evidence of underlying lung disease such as nodular bronchiectasis and/or fibrocavitary disease by chest radiography or chest computed tomography. High resolution CT (HRCT) scan is preferred, if available
4. have a MAC lung infection documented by at least 2 positive cultures (MAC or mixed infection with MAC as the dominant species), consisting of at least one obtained within 6 months prior to Screening and one positive culture at Screening (cultures to be at least 1 month apart). Cultures may be obtained from sputum or bronchoscopy.
5. have a MAC-positive sputum at Screening
6. be willing to adhere to multi-drug treatment regimen during the course of the study
7. be able to produce approximately 3 mL of sputum or be willing to undergo an induction that produces approximately 3 mL of sputum for mycobacteriology
8. female of child bearing potential agrees to practice an acceptable method of birth control (e.g., true abstinence [refraining from heterosexual intercourse during the entire study], hormonal or barrier methods, partner sterilization, or intrauterine device [IUD]) while participating in the trial. Periodic abstinence (e.g., calendar, ovulation, symptothermal, post-ovulation methods), declaration of abstinence for the duration of the study, and withdrawal are not acceptable methods of contraception.

Protocol Amendment #3 version: 22 February 2016

*This protocol is solely for the purpose of communicating information about the investigational drug between Insmmed Incorporated and study personnel. Information is not to be reproduced, abstracted or used for sharing of information for any other purpose, whatsoever, except with the written permission of Insmmed Incorporated.*

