#### **4.2 EXCLUSION CRITERIA**

A prospective patient with any of the following conditions must be excluded from this study:

1. patients with cystic fibrosis
2. patients whose MAC NTM infection is resistant to amikacin (as identified by MIC susceptibility  $>64 \mu\text{g/mL}$ )
3. patients who are not able to perform the 6MWT
4. positive pregnancy test or lactation at Screening. All women of child bearing potential will be tested. Women not of child bearing potential are defined as postmenopausal (i.e., amenorrheic for at least 1 year), or surgically or naturally sterile.
5. active pulmonary malignancy (primary or metastatic) or any malignancy requiring chemotherapy or radiation therapy within 1 year before Screening or anticipated during the study period
6. active allergic bronchopulmonary mycosis or any other condition requiring chronic systemic corticosteroids at a dose greater than the equivalent of 10 mg/day of prednisone within 3 months before Screening
7. active pulmonary tuberculosis requiring treatment at Screening
8. history of lung transplantation
9. initiation of chronic therapy (e.g., high dose ibuprofen, inhaled anti-inflammatory agents including steroids, low dose maintenance steroids, rhDNase) within 28 days before Day 1
10. administration of any investigational drug within 8 weeks before Screening

Protocol Amendment #3 version: 22 February 2016

*This protocol is solely for the purpose of communicating information about the investigational drug between Insmmed Incorporated and study personnel. Information is not to be reproduced, abstracted or used for sharing of information for any other purpose, whatsoever, except with the written permission of Insmmed Incorporated.*

11. prior exposure to LAI (including clinical study)
12. known hypersensitivity to aminoglycosides
13. use of inhaled or systemic aminoglycosides with activity against MAC (e.g., amikacin, kanamycin, or streptomycin) within 28 days before Day 1
14. acquired and primary immunodeficiency syndromes (e.g. HIV-positive patients regardless of CD4 counts)
15. significant (as determined by the investigator) hearing loss, vestibular dysfunction, neuromuscular weakness or a diagnosis of myasthenia gravis, where the potential risk of aminoglycoside toxicity outweighs the potential benefit
16. aspartate aminotransferase or alanine aminotransferase  $\geq 3$  times the upper limit of normal (ULN) or total bilirubin  $\geq 2$  times ULN at Screening

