## 5.9 CONCOMITANT MEDICATIONS

Throughout the duration of the study, subjects should continue on the same, multi-drug (at least 2 antibiotics), anti-mycobacterial regimen. The regimen should be based on the 2007 ATS/IDSA Guidelines or respective local guidelines, and should not change during the treatment period except for safety concerns or if “rescue” anti-mycobacterial therapy is required. Any subject who has to have “rescue” medication will be discontinued. All NTM treatment should stop at the EOT visit. No NTM treatment should be given during the safety follow-up period.

Where allowed, and if approved by IRB/EC, the sponsor will provide reimbursement of the multi-drug anti-mycobacterial regimen for as long as the patient participates in the study and is adherent to all protocol requirements. These drugs may include, but are not limited to: azithromycin, clarithromycin, clofazimine, ethambutol, ethionamide, rifabutin, and rifampicin.

Protocol Amendment #3 version: 22 February 2016

*This protocol is solely for the purpose of communicating information about the investigational drug between Insmmed Incorporated and study personnel. Information is not to be reproduced, abstracted or used for sharing of information for any other purpose, whatsoever, except with the written permission of Insmmed Incorporated.*

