## 5.11 PRECAUTIONARY MEDICATIONS

Treatment with oral or IV antibiotics (other than the subject’s stable anti-mycobacterial regimen) for acute pulmonary exacerbations or acute infection is allowed as determined by the Investigator; the reason for use must be documented in the eCRF (electronic case report form). Intra-muscular antibiotics that do not have activity against MAC (see prohibited medications) are permitted and must be documented in the eCRF.

Chronic anti-inflammatory therapy (e.g., high-dose ibuprofen, prednisone  $\leq$  10 mg/day or the equivalent) is permitted if the regimen remains unaltered for at least 28 days preceding Day 1 and throughout the study. The doses should not change except for safety reasons or as needed for medical management of the subject.

Although systemic exposure to amikacin is low after LAI administration, precaution should be taken if subjects require the following systemic medications that may have possible interactions

Protocol Amendment #3 version: 22 February 2016

*This protocol is solely for the purpose of communicating information about the investigational drug between Insmmed Incorporated and study personnel. Information is not to be reproduced, abstracted or used for sharing of information for any other purpose, whatsoever, except with the written permission of Insmmed Incorporated.*

with amikacin: potent diuretics (such as ethacrynic acid and furosemide), beta lactam antibiotics (such as penicillins and cephalosporins); bisphosphonates; platinum compounds and thiamine.

Bronchodilator therapy is allowed. Subjects who develop bronchospasm may be pre-treated with a bronchodilator before study drug administration.

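### The background anti-mycobacterial regimen is not fixed before open-label allocation, so the Day 1 choice, chiefly for subjects who start one, can be made with the arm known

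*Protocol*

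**What the plan says.** **Timing.** The Protocol synopsis (Study Description) says: "At Baseline, subjects will start or continue on a multi-drug anti-mycobacterial regimen (at least 2 antibiotics) and will be randomized". Section 5.6 provides no blinding, and Section 9.3 gives 2:1 open-label allocation. No section says whether the regimen is chosen before or after the allocation is released.

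**Population.** The synopsis and Section 1.2 describe subjects "refractory to a stable multi-drug regimen for at least 6 months". Inclusion criterion 2 (Section 4.1) asks for at least two antibiotics "for a minimum duration of 6 consecutive months that is either ongoing or was stopped no more than 12 months before Screening", with exceptions for tolerability. It does not ask that this regimen be unchanged, or that it be the one used in the study.

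**During the study.** Section 5.9 says: "Throughout the duration of the study, subjects should continue on the same, multi-drug (at least 2 antibiotics), anti-mycobacterial regimen". The regimen is to follow the 2007 ATS/IDSA or local guidelines, and "should not change during the treatment period except for safety concerns" or a need for rescue therapy. Rescue leads to discontinuation.

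**Rules before Day 1 for other drugs.** Section 5.11 says chronic anti-inflammatory therapy "is permitted if the regimen remains unaltered for at least 28 days preceding Day 1 and throughout the study". Exclusion criterion 9 bars "initiation of chronic therapy (e.g., high dose ibuprofen, inhaled anti-inflammatory agents including steroids, low dose maintenance steroids, rhDNase) within 28 days before Day 1". Exclusion criterion 13 bars aminoglycosides active against MAC in the 28 days before Day 1.

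**What is recorded.** Section 6.1 lets concomitant medications be asked about at any time between Screening and Baseline, and enters them in the EDC system only once the subject is enrolled. Randomization is stratified by smoking and by "current multi-drug regimen status (on treatment or off treatment for at least 3 months) at Screening". That records whether a regimen is being taken, not which drugs are in it.

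**The concern.** The background regimen is the whole treatment in the control arm and half of the comparison in the LAI arm. The investigator selects it, and the trial is open-label. If the drugs can be chosen after the arm is seen, a control subject might be given a fuller regimen to compensate, or an LAI subject a lighter or heavier one.

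That would be a real difference in co-treatment. Central culture reading would not remove it, because the cultures themselves would differ. Randomization and stratification balance what is true at Screening, not what is decided after allocation. The converter definition (Section 4.6) and the primary analysis (Section 9.6.1) set no condition on the regimen, so any resulting conversion counts.

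A second, weaker question concerns the 10 to 14 week Screening period. If a drug is added after the Screening sputum, the qualifying positive culture no longer reflects the regimen carried into the study.

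**Working it through.** **Where the window is open**

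| Situation | Rule in the Protocol | Still open? |
|---|---|---|
| After Day 1, all subjects | 5.9: no change except for safety or rescue; rescue leads to discontinuation | No |
| Day 1, on treatment | 5.9: continue on the same regimen | Arguably closed, but 5.9 does not say from when *the same* is counted |
| Day 1, off treatment | Synopsis: starts a regimen at Baseline | Yes: there is no current regimen to continue, and no order relative to allocation |
| Screening period, on treatment | 5.9, if Screening is part of the study | Unclear: 3.6.2 counts Screening within the time in the study, but 7.2.6.1 and 7.2.8 begin the study period at Day 1 |
| MAC-active aminoglycosides | Exclusion 13 and Section 5.10 | No |

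**The plan's sample size**

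Inputs from Section 9.1: control p1 = 0.05, LAI p2 = 0.20, ratio r = 2, two-sided 0.05, 90% power, continuity-corrected chi-square. Pooled p = (0.05 + 2 × 0.20)/3 = 0.15, and d = 0.15.

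- Uncorrected: n1 = [1.960 √(1.5 × 0.15 × 0.85) + 1.2816 √(0.05 × 0.95 + 0.20 × 0.80/2)]² / 0.15² = 76.8.
- Corrected: n1 = (76.8/4) × [1 + √(1 + 2 × 3/(76.8 × 2 × 0.15))]² = 86.5, so 87 control, 174 LAI and 261 in total.

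The stated 261 is reproduced; there is no arithmetic error.

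Power at 87/174 = Φ[(d − cc − 1.960 × SE0)/SE1], where cc = (1/87 + 1/174)/2 = 0.0086, and SE0 and SE1 are the standard errors of the difference with pooled and with separate rates. At 5% against 20%: (0.15 − 0.0086 − 1.960 × 0.0469)/0.0383 = 1.29, which is 90.2%.

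**Sensitivity, by assumption only**

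The Protocol gives no share of subjects starting a regimen and no conversion rate on a new one. Let a share f of controls receive a regimen that converts a proportion q, and leave LAI at 20%. The control rate is then (1 − f) × 0.05 + f × q.

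| f | q | Control rate | Power at 261 |
|---|---|---|---|
| 0 | – | 5% | 90.2% |
| 10% | 10% | 5.5% | 87.1% |
| 10% | 20% | 6.5% | 79.6% |
| 25% | 10% | 6.25% | 81.6% |
| 25% | 20% | 8.75% | 58.3% |
| 50% | 20% | 12.5% | 25.0% |

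In the 25%/20% row the expected difference shrinks from 15 to 20 − 8.75 = 11.25 points.

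The other direction: suppose LAI has no effect and 25% of one arm only receives a regimen converting 20%. The rates are 8.75% against 5%, a spurious difference of 3.75 points. By exact enumeration of the corrected chi-square, the two-sided test rejects in 9.7% of trials if the LAI arm is the favoured one and in 16.7% if the control arm is. With 5% in both arms it rejects in 2.1%.

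If both arms gain equally (10% against 25%), the difference stays at 15 points and power falls to 79.9%. That costs precision but introduces no bias.

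These figures use an unstratified test at the planned 261; the primary analysis is a stratified Cochran-Mantel-Haenszel test on all randomized subjects.

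**The case against.** The strongest reply is Section 5.9. A reader might infer from the synopsis that the comparator can be strengthened at any time once the arm is known. The Protocol does not support that: after treatment begins only safety or rescue justifies a change, and rescue ends participation. For subjects already on treatment, the instruction to continue on the same regimen can be read as covering Day 1 and, if Screening counts as part of the study, the weeks before it. This stands, and it narrows the point to the Day 1 choice.

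A reader might also infer that anti-mycobacterial drugs have no rule before Day 1. That is wrong for MAC-active aminoglycosides (exclusion 13), and the guideline requirement bounds the rest. It bounds the choice without fixing it, since local guidelines are admitted and only a minimum of two antibiotics is set.

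A third tempting inference is that conversion on a newly started regimen falls outside the trial's question. Criterion 2 deliberately admits subjects who stopped treatment up to 12 months before Screening, and the objective compares LAI added to a regimen with a regimen alone. If starting a regimen works alike in both arms, randomization balances it. The problem is only a choice that differs by arm.

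Finally, medications are asked about from Screening, so a Day 1 change in a subject on treatment should show in source records. That helps detection. It does not help for a subject with no current regimen, and it does not record what was intended before allocation. Sites also do not see culture results until after the Month 6 result is known (Section 3.1), which limits later culture-driven changes but not the Day 1 choice.

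**Conclusion.** The point holds in a limited form. Nothing in the Protocol fixes the content of the background regimen before open-label allocation, and the *stable* regimen of the rationale is not an entry criterion. The gap is clear for subjects off treatment who start a regimen at Baseline. It is doubtful for subjects already on treatment and for changes during Screening.

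A choice made with the arm known could bias the primary endpoint either way: a stronger control regimen hides an effect, and a stronger LAI-arm regimen mimics one. The documents do not show that this would happen or how often. The power and rejection figures above depend wholly on assumed shares and conversion rates. They show only that a design planned on a 5% control rate is sensitive to a few points. It is worth correcting because the safeguard is nearly free and cannot be added at the analysis stage.

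**What to change.** 1. Require the site to enter the intended Day 1 multi-drug regimen, by drug name, in the IWRS before the system releases the allocation. State this in Sections 3.6.4 and 5.9.
2. Record any departure from that entry on Day 1 that is not for safety as a protocol deviation.
3. Reconcile the four descriptions: *stable* (synopsis and Section 1.2), *start or continue* (synopsis), inclusion criterion 2 (Section 4.1) and *the same* regimen (Section 5.9). Say from which time point the regimen counts as the same, and whether Screening is included. Which stability rule applies is for the sponsor to decide; this review proposes none.

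The cost is one field in a system already in use, plus wording in the sections named. The entry prescribes no drug.
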